5.2.3 ECG

5.2.3.1 Resting 12-lead ECG

12-lead pECG recordings will be collected as detailed in [Table 1](#). The investigator will make an overall evaluation of the pECG as normal or abnormal. If abnormal, it will be decided whether or not the abnormality is clinically significant or not clinically significant and the reason for the abnormality will be recorded on the eCRF.

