3.2 Exclusion criteria

Subjects should not enter the study if any of the following exclusion criteria are fulfilled:

- 1 History or current inflammatory rheumatic disease other than RA (secondary Sjogren's syndrome excluded)
- 2 History or current clinically important disease which may either put the subject at risk because of participation in the study, or influence the results or the subject's ability to participate in the study
- 3 Any clinical contraindications to treatment with steroids
- 4 Oral or parenteral steroids (beyond study medication) 8 weeks prior to study start and during the study. Stable use and dose of topical and inhaled steroids for longer than 4 w prior to randomisation is acceptable
- 5 Use of any prohibited medication during the study or if the required washout time of such medication was not adhered to (for details see Section [7.7.1](#))
- 6 History of severe allergy/hypersensitivity or ongoing clinically important allergy/hypersensitivity to drugs with a similar class to study drugs
- 7 Any concomitant medications that are known to be associated with Torsades de Pointes, for additional information see Section [7.7.1](#))
- 8 Any clinically significant ECG; vital signs or laboratory abnormalities identified at screening or prior to randomisation
- 9 Known history of drug or alcohol abuse within 1 year of screening
- 10 Involvement in the planning and/or conduct of the study (applies to both AstraZeneca staff and/or staff at the study site)
- 11 Previous randomisation in the present study
- 12 Participation in another clinical study with an investigational product during the last 3 months

In addition, any of the following is regarded as criteria for exclusion from the genetic research:

- 13 Previous bone marrow transplant
- 14 Whole blood transfusion within 120 days of the date of genetic sample collection

Procedures for withdrawal of incorrectly enrolled subjects see Section [3.4](#).

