4. STUDY PLAN AND TIMING OF PROCEDURES

Table 1 Study Plan detailing the procedures

Study procedures	Screening Visit 1	Day 1 Visit 2 (within 1 week of V1)	Day 5 Phone call Visit 3	Day 8 +/- 1 Visit 4	Day 15 +/- 1 EOT ^a Visit 5	Day 28 +/- 2 Follow-up Visit 6
Inclusion/exclusion criteria	X					
Demographic data	X					
Medical history (incl. RA history and oral health)	X					
Concomitant medication	X	X	X	X	X	X
Informed consent	X					
Informed consent for genetic sample	X					
Randomisation		X				
Study drug dispensation		X ^b		X		
Study drug administration:		X ^b	→	→ NB: at site	X NB: at site	
Study drug return					X	
Adverse events		X	→	→	→	X
Serious adverse events	X	→	→	→	→	X
Vital signs (BP/P and body temperature)	X	X ^d		X	X	X
12-lead ECG	X	X ^{d, f}			X	X
Clinical laboratory evaluations (Haematology, serum biochemistry, endocrinology ^e , and urine ^e analysis)	X ^c	X ^d		X ^d	X ^d	X
Pregnancy test (serum)	X					X
Erythrocyte sedimentation rate, ESR (at site)	X	X ^d		X ^d	X ^d	X
Physical examination,	X	X		X	X	X
Body weight & height ^e	X				X	X
DAS28-CRP	X	X ^d		X	X	X
ACR20, 50, and 70	X	X ^d		X	X	X
SJC and TJC 66/68	X	X ^d		X	X	X
Blood sampling for exploratory biomarkers (cortisol, serum)		X ^{d,g} Profile: 0, 1, 2, 3, 4 and 6 h			Pre dose ^g & 1, 2, 3, 4 and 6 h post dose	
Blood sampling for exploratory biomarkers (LPS stimulated TNF α , whole blood)		X ^d Profile: 0, 1, 2, 3, 4 and 6 h			Pre dose & 1, 2, 3, 4 and 6 h post dose	
Blood sample (whole blood) for mRNA ⁱ		X ^d			X ^h	

Table 1 Study Plan detailing the procedures

Study procedures	Screening Visit 1	Day 1 Visit 2 (within 1 week of V1)	Day 5 Phone call Visit 3	Day 8 +/- 1 Visit 4	Day 15 +/- 1 EOT ^a Visit 5	Day 28 +/- 2 Follow-up Visit 6
Blood sample for other potential biomarkers (serum)		X ^d			X ^d	X
Blood sample for DNA (future exploratory research)		X ^b				
Blood sampling for PK of AZD9567/ prednisolone					Pre-dose, 0.25, 0.5, 1, 1.5, 2, 3, 4 and 6 h	

^a End of treatment

^b After randomisation

^c Local lab

^d Pre-dose

^e Only at Visit 1

^f Only performed if Visit 1 was >3 days ago

^g Preferably starting as close to 08.00 as possible

^h At 1h post dose (C_{max})

ⁱ A peripheral blood mononuclear cell method may be used at selective site/s

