4.2 Treatment period

At Visit 2, the pre-dose/baseline assessments will be performed. Thereafter the patients will be randomised 1:1 to receive either 40 mg AZD9567 or 20 mg prednisolone. The treatment period is 2 weeks. Patients will receive IMP to bring home sufficient for one week treatment. They will also receive handling instructions in local language detailing how to take the IMP. Double dummy technique is applied as the IMP has different formulations, see [Section 0](#). The site staff will call the patients 5 days after start of treatment and ask for possible adverse events. This phone call will be called Visit 3 in the eCRF. This precaution is taken to ensure the safety of the patients as 5 days is the longest treatment regimen so far in a clinical study with AZD9567. Patients will then come back to the clinic after one week, Visit 4, to receive medication for the last week and to perform study assessments. After two weeks of treatment the end of treatment visit, Visit 5, will be performed. For details, see [Table 1](#).

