7.2 Dose and treatment regimens

A total of 40 eligible patients will be randomly assigned 1:1 to the study treatment. This will be managed via IWRS. The dose of IP, AZD9567 40 mg and prednisolone 20 mg, will be

taken once daily (in the morning) for 14 days. Detailed instructions are provided in the Handling instructions each patient will be provided with in local language. The first dose of IMP will be taken at the clinic after the baseline assessments have been performed on Visit 2. Also at the end of treatment visit, Visit 5, the IMP should be taken at the site to allow for a pre dose blood sample to be drawn for PK analyses. As the IMP has different formulations, double dummy technique is applied. Each patient will therefore take both oral suspension and 4 capsules of prednisolone/placebo on a daily basis for 14 days. The oral suspensions of AZD9567 and placebo are not taste neutral. This information will be included in the Patient Informed Consent form. Opening aids for the IMP bottles will be supplied by AstraZeneca and will be described in the Handling instructions.

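### The only on-treatment ECG (Visit 5) has no set time relative to the dose, and for completers it does not enter the SAP's ECG shift table

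*Protocol*

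**What the plan says.** ECG is a named safety outcome in Protocol section 2.3 and SAP section 1.1.3. For timing, Protocol section 5.2.3.1 states only that "12-lead pECG recordings will be collected as detailed in" Table 1, and SAP section 3.4.3 also points back to Table 1.

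The ECG row of Table 1 has entries at Visits 1, 2, 5 and 6 and none at Visits 3 and 4. The Visit 2 entry is marked pre-dose and is conditional: "Only performed if Visit 1 was >3 days ago". The Visit 5 entry has no footnote.

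Other Visit 5 procedures are timed. Laboratory tests and ESR are marked pre-dose. PK samples are set at "Pre-dose, 0.25, 0.5, 1, 1.5, 2, 3, 4 and 6 h". Cortisol and TNFα samples have their own hours. The mRNA sample is taken "At 1h post dose", a time that footnote h identifies with Cmax. Protocol section 7.2 explains that at Visit 5 "the IMP should be taken at the site to allow for a pre dose blood sample to be drawn for PK analyses".

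The reading is an investigator's overall rating: normal, abnormal but not clinically significant, or abnormal and clinically significant. SAP section 4.8.6.5 tabulates the shift in this rating from baseline to the last post-baseline ECG and lists every recording. SAP section 4.8.6 drops the QTcF tables because the data were not planned for the eCRF.

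**The concern.** Each patient has one chance of an ECG on drug. The protocol notes that "5 days is the longest treatment regimen so far in a clinical study with AZD9567", so this trial gives the first ECGs after longer dosing. It also treats QT risk as relevant when choosing patients, by excluding "Any concomitant medications that are known to be associated with Torsades de Pointes". If the one on-drug recording is made on arrival, with the other pre-dose procedures, it describes trough exposure. A normal trough reading says less about the hours around the peak, and without a set or recorded time a reader cannot tell which kind of reading it is.

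The analysis adds a second gap. If the summary table takes the follow-up ECG, it describes patients who have been off drug for about two weeks, and the on-drug recording is not summarised.

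**Working it through.** No stated figure is at issue, so the check is of the schedule, with one illustrative calculation.

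**Step 1. Which scheduled ECGs are on drug?** (Protocol Table 1)

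| Visit | ECG | Relation to dosing |
|---|---|---|
| 1 | Yes | Before first dose |
| 2 | Conditional | Pre-dose, before first dose |
| 3 | No | Telephone call |
| 4 | No | On treatment, no ECG |
| 5 | Yes | Day 15 ± 1, dose on site, ECG time not stated |
| 6 | Yes | Day 28 ± 2, off drug |

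Taking the last dose at Visit 5, Visit 6 falls 28 − 15 = 13 days later at the nominal days. The windows allow 26 − 16 = 10 to 30 − 14 = 16 days. On-drug ECGs per patient: one.

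**Step 2. What times does the plan allow for it?** Dosing is once daily in the morning (Protocol section 7.2), so the time before the Visit 5 dose is about 24 h after the previous one. Protocol section 8.5.2.1 treats it the same way, using the pre-dose concentration as the 24 h value. Footnote h puts Cmax at 1 h. A pre-dose ECG is therefore 24 − 1 = 23 h past the expected peak. Sampling keeps the patient on site until 6 h post-dose, so a recording near the peak is equally feasible. The plan requires neither.

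**Step 3. How different could exposure be?** The documents give no half-life, so these values are assumptions. With mono-exponential decline from 1 h, the ratio is C(24 h)/C(1 h) = 2^(−23/t½). Accumulation on repeated dosing cancels, because both times lie in the same dosing interval.

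| Assumed t½ | Exponent | C(24 h) as share of C(1 h) |
|---|---|---|
| 3 h | −7.67 | 0.5% |
| 4 h | −5.75 | 2% |
| 6 h | −3.83 | 7% |
| 8 h | −2.88 | 14% |
| 12 h | −1.92 | 26% |
| 24 h | −0.96 | 51% |

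**Step 4. Where does the Visit 5 result go?** The shift table in SAP section 4.8.6.5 uses the last post-baseline ECG. A completer has ECGs at Visits 5 and 6, and the later one is used. Visit 5 enters the table only for a patient with no Visit 6 (or later unscheduled) ECG.

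**Step 5. Count per completer.**

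| | As written | With both changes |
|---|---|---|
| On-drug ECGs scheduled near 1 h | 0 | 1 |
| On-drug ECGs entering a shift table | 0 | 1 |

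**The case against.** Several points on the other side stand.

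- **Trough timing is permitted, not required.** A site could record near the peak, and any site ECG instructions are outside the reviewed documents. A reader might infer that the ECG will be taken at trough; the text shows only that nothing prevents it.
- **The summary does not mix trough and peak readings.** A reader might infer that uneven site timing contaminates the shift table. For completers it does not, because the table uses Visit 6. For the same reason, the Visit 5 readings are not summarised as reassurance. Setting the time alone would leave them out, so the SAP must change too.
- **No ECG signal is documented.** The exclusion of drugs linked to Torsades de Pointes restricts co-medication and does not state that AZD9567 affects QT. Protocol sections 1.2 and 1.3 describe single doses up to 155 mg and multiple doses up to 80 mg as well tolerated, without giving ECG results. A reader might infer that a peak effect is being missed; the documents do not show that one exists.
- **The reading is coarse.** A modest QT change at 1 h could still be rated normal, and better timing does not alter that.
- **The 1 h Cmax rests on one footnote,** and tmax is itself to be estimated from samples between 0.25 and 6 h.
- **Numbers are small and recruitment closed early.** SAP section 1.3 gives 10 per group, and SAP section 6 records the early closure. A footnote cannot change ECGs already taken.

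These points limit the size of the gain. They do not supply the missing time or bring the on-drug reading into the table.

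**Conclusion.** The concern holds in limited form. The plan schedules one on-drug ECG per patient, guarantees none near its own 1 h Cmax point, and for completers leaves that ECG out of the only ECG summary table. These findings come from the schedule and the SAP's last-observation rule and need no pharmacokinetic assumption.

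The loss in exposure if the ECG is taken at trough does depend on assumptions. With mono-exponential decline and half-lives of 3 to 24 h, the trough is about 0.5% to 51% of the 1 h level, so it could be large or moderate.

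This is a low-cost improvement to a qualitative safety reading. It is not evidence of a missed cardiac effect, and it would not make the study able to measure QTc.

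**What to change.** Two changes, made together:

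1. Add a footnote to the Visit 5 ECG entry in Protocol Table 1 setting the recording at 1 h post-dose, just before that blood draw, with the clock time entered on the eCRF.
2. In SAP section 4.8.6.5, present an on-treatment shift from baseline to Visit 5 separately from the shift to Visit 6.

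The cost is one footnote, one eCRF time field and one extra table. No ECG, visit or blood sample is added. The downside is a slightly busier 1 h point, which already carries the PK, cortisol, TNFα and mRNA draws. For ECGs already recorded, only the SAP change can help. It would bring the on-drug readings into a table, but their time relative to the dose would stay unknown unless it was captured at the time.

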3.4.3 ECG

Twelve-lead ECGs will be obtained at the times indicated in the Study Plan and Timing of Procedures (refer to protocol Table 1). An overall evaluation (normal, abnormal not clinically significant, and abnormal clinically significant) with a reason for abnormality will also be recorded.

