4.8.6 Safety

Safety and tolerability summaries will be presented using the SAF, unless other specified.

The following tables, required by the AZ corporate standards, will not be provided for this study because the relevant data were not planned to be collected on the eCRF.

Urinalysis, baseline versus maximum value on treatment, shift table (<<analysis set>>)
Urinalysis, treatment-emergent changes (<<analysis set>>)
QTcF and QTcF intervals, at <<last>> any observation on treatment (<<analysis set>>)
Electrocardiogram results exceeding ICH reference range boundaries (<<analysis set>>)

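### ECGs are scheduled, but only a qualitative evaluation is captured, and the one planned ECG table usually shows the off-drug Day 28 trace, so on-treatment interval change is not summarised

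*Protocol*

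**What the plan says.** **Outcome and schedule.** Protocol 2.3 and SAP 1.1.3 list ECG among the safety outcomes. Protocol Table 1 schedules a 12-lead ECG at Visit 1, Visit 2, Visit 5 (end of treatment, Day 15) and Visit 6 (follow-up, Day 28). The Visit 2 ECG is pre-dose and is done only if Visit 1 was more than 3 days earlier. No time relative to dose is given for the Visit 5 ECG.

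**What is recorded.** Protocol 5.2.3.1: "The investigator will make an overall evaluation of the pECG as normal or abnormal". The same section has the investigator grade an abnormal trace for clinical significance and note why it is abnormal. SAP 3.4.3 makes this a three-level variable: "An overall evaluation (normal, abnormal not clinically significant, and abnormal clinically significant) with a reason for abnormality will also be recorded". Neither section names heart rate, PR, QRS, QT or QTcF.

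**What is analysed.** SAP 4.8.6 lists corporate-standard tables that "will not be provided for this study because the relevant data were not planned to be collected on the eCRF". They include the table of "QTcF and QTcF intervals" and the table of ECG results outside ICH boundaries. SAP 4.8.6.5 leaves one ECG table, a shift in the evaluation category from baseline to the last post-baseline observation, plus a listing of every ECG.

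**Context.** Dosing lasts 14 days (Protocol 7.2), and Protocol 4.2 notes that "5 days is the longest treatment regimen so far in a clinical study with AZD9567". Exclusion criterion 7 covers "Any concomitant medications that are known to be associated with Torsades de Pointes", and Protocol 7.7.1 points to guidance on avoiding QT-prolonging drugs.

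**The concern.** Two losses combine. First, an ECG is reduced to a category and, if abnormal, a reason. An interval can change without moving the patient from one category to another, and nothing in the dataset would then show it. Exclusion criterion 8 removes clinically significant ECG abnormalities at entry, so patients should start as normal or as abnormal but not clinically significant. Change within those two categories is what the plan cannot see.

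Second, the one table that uses the category looks at the wrong time for most patients. The last post-baseline ECG of anyone who attends follow-up is the Visit 6 trace, taken about two weeks after the last dose.

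At stake is the ECG part of the safety objective, in the first patients to receive the compound and the first exposure longer than 5 days. Laboratory values and vital signs get observed values and change from baseline by visit (SAP 4.8.6.3 and 4.8.6.4). ECG does not.

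**Working it through.** The documents give no ECG figure (no SD, threshold or power), so there is nothing to reproduce. The check is textual, followed by an illustration of what interval data could deliver.

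**Step 1. Are intervals collected?** Protocol 5.2.3.1 and SAP 3.4.3 name only the evaluation, its significance grade and a reason. On their own they show only that intervals are not mentioned. SAP 4.8.6 settles it: the interval tables are dropped because the data were not planned for the eCRF. No other reason is given.

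**Step 2. Which ECG enters the shift table?** There are two scheduled post-baseline ECGs, Visit 5 (Day 15 ± 1) and Visit 6 (Day 28 ± 2). For a patient with both, the last is Visit 6, nominally 28 − 15 = 13 days after the final dose. For a patient who withdraws between the two visits, the last is Visit 5. The post-baseline column therefore mixes off-drug traces (completers) with any on-treatment traces from early withdrawals, and a completer's Visit 5 result is only listed.

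**Step 3. What could interval data show?** Inputs: n = 10 per arm (agreed number, SAP 1.3) or 20 per arm (planned number, same section). The SD of the change in QTcF is an assumption, taken as 10, 15 and 20 ms.

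- Within-arm 95% half-width = t(0.975, n−1) × SD / √n. For n = 10 and SD = 10: 2.262 × 10 / √10 = 7.2 ms.
- Between-arm 95% half-width = t(0.975, 2n−2) × SD × √(2/n). For n = 10 and SD = 10: 2.101 × 10 × √0.2 = 9.4 ms.

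| n per arm | Assumed SD (ms) | Within arm (ms) | Between arms (ms) |
|---|---|---|---|
| 10 | 10 | 7.2 | 9.4 |
| 10 | 15 | 10.7 | 14.1 |
| 10 | 20 | 14.3 | 18.8 |
| 20 | 10 | 4.7 | 6.4 |
| 20 | 15 | 7.0 | 9.6 |
| 20 | 20 | 9.4 | 12.8 |

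**Step 4. Would an outlier count do instead?** With no outliers among n patients, the one-sided 95% upper bound on the outlier rate is 1 − 0.05^(1/n), which is 25.9% at n = 10 and 13.9% at n = 20. The ICH-boundary table alone would thus say little. Neither dropped table mentions change from baseline in its title, so restoring both would not by itself supply a change summary.

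**Step 5. Workload.** At most 4 ECGs per patient: 4 × 20 = 80 transcriptions at 20 patients, 4 × 40 = 160 at 40.

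**The case against.** The best defence is that the plan does what it set out to do. ECG is named as an outcome without any interval measure, the SAP analyses the variable as defined, and the omission is disclosed. Protocol and SAP do not contradict each other. That stands: this is a design choice, not an error.

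Four stronger readings are tempting, and the documents do not support them.

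- *The record is only normal or abnormal.* It has three levels plus a reason, and every ECG is listed. A prolongation that the investigator judged abnormal would appear.
- *The QT-related restrictions imply a QT problem with AZD9567.* The exclusion and the guidance concern co-medication. Protocol 1.3 lists potential effects on glucose and lipid metabolism, bone metabolism and inflammation, and reports good tolerability in healthy volunteers. Whether intervals were measured in the earlier studies cannot be seen from these documents.
- *Collecting intervals would let the trial exclude a QT effect.* It would not. At 10 per arm the between-arm half-width is 9 to 19 ms under the assumed SDs. Without a placebo arm, the within-arm change is uncontrolled.
- *The ECG objective goes unanswered.* It is answered qualitatively. What is missing is quantitative change and an on-treatment summary.

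Two practical objections also stand. The Visit 5 ECG is not timed to dose, and neither replicate recording nor central reading is specified, so the intervals would be noisy. Nor do the documents say that traces are retained for later reading.

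None of this answers the timing fault in the shift table, which needs no interval data to correct.

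**Conclusion.** The point holds as a modest, low-cost improvement. Interval data are not captured, and the only stated reason for dropping two standard tables is that the eCRF does not hold them. The single remaining ECG table reports, for patients who complete follow-up, a trace taken about two weeks off drug. Both conclusions rest on the text alone.

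The size of the gain rests on an assumed SD of 10 to 20 ms for the change in QTcF. On that assumption, at 10 per arm, a summary would carry a 95% half-width of about 7 to 14 ms within arm and 9 to 19 ms between arms. That suits a descriptive safety table and could reveal a large shift. It could not exclude a modest one. The primary efficacy analysis is unaffected.

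**What to change.** 1. **eCRF.** Add heart rate, PR, QRS, QT, QTcF and ECG clock time to the ECG page, filled from the ECGs already scheduled. If recruitment has closed (SAP section 6 refers to early closure), do this retrospectively, only where traces were retained, and before unblinding. Clock time lets the Visit 5 reading be set against that day's PK samples, which run from pre-dose to 6 h.
2. **Baseline.** State for ECG that baseline is the last pre-dose trace: Visit 2 if done, otherwise Visit 1. This agrees with the general rule in SAP 4.1.2.
3. **Interval tables.** In SAP 4.8.6.5, add a descriptive summary of observed values and change from baseline to Visit 5 by arm. Reinstate the two standard tables listed as omitted in SAP 4.8.6. Label all of these as descriptive.
4. **Shift table.** Present the categorical shift from baseline to Visit 5 as well as to the last observation. This needs no new data.

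**Cost.** One eCRF page revision, a short SAP amendment, and transcription of at most 80 ECGs at 20 patients or 160 at 40. No new visit or procedure is needed. The downside is noise from site-read single ECGs not timed to dose, which the report should acknowledge beside the table.

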5.2.4 Vital signs

Vital signs will include pulse, and systolic and diastolic blood pressure as well as body temperature. Vital signs will be obtained at timepoints indicated in [see Table 1](#) (and ad-hoc as medically indicated).

